6.5.3 Subgroup Analysis

The efficacy analyses will be performed by stratifying for the following subgroups:

- Subjects aged “6 through 23 months” and “24 through 47 months”.
- Subjects “previously influenza vaccinated” and “not-previously influenza vaccinated”.
- Subjects by race.
- Subjects by gender.
- Subjects by country or region.
- Subjects by season/year treated.

Statistical Analysis Plan – Final v2.0

Sponsor Name: Seqirus UK Limited
Sponsor Protocol ID: V130_14

6.6 Immunogenicity

6.6.1 Secondary Immunogenicity Endpoints Analysis

Secondary immunogenicity objectives will be evaluated based on the PPS Immunogenicity HI, PPS Immunogenicity MN, FAS Immunogenicity HI and FAS Immunogenicity MN.

No statistical testing will be performed for the comparative secondary immunogenicity objectives.

All statistical analyses for HI (or MN titers) will be performed on the logarithmically (base 10) transformed values. Individual HI titers below detection limit (<10) will be set to half of that limit (5). Individual MN titers below the lower limit of quantification (LLOQ), will be set to half of that limit (1/2* LLOQ).

Crude estimates for GMTs, GMRs and pertaining 2-sided 95% CIs will be calculated assuming log-normal distribution of the titers and will be completed by providing minimum, maximum and median titers for each study vaccine group.

Binary data (i.e., percentages of subjects with SCR and with titer $\geq 1:40$) will be summarized for each group using crude estimates and will be reported together with 2-sided 95% CIs calculated according to Clopper's and Pearson's (1934) method. No multiplicity adjustment to the CI levels will be implemented.

For immunogenicity data, it may be reasonable to consider missing immunogenicity values as missing completely at random (MCAR), i.e., not informative. Therefore, the key secondary analysis will comprise a complete case analysis only, without introducing any bias. Imputation methods will not be used.

Derived variables:

Values below the limit of quantification (LQ = 10) recorded as "< LQ" and values lower than the limit of quantification have been set to half that limit (5).

The rate of seroconversion is defined as the percentage of subjects with either a prevaccination HI (or MN) titer $< 1:10$ and a post vaccination HI (or MN) titer $\geq 1:40$ or a prevaccination HI (or MN) titer $\geq 1:10$ and a ≥ 4 -fold increase in post vaccination HI (or MN) titer.

Seroconversion is defined as binary variable for subjects with non-missing values prevaccination and post-vaccination as:

= 1, if seroconverted (defined as the percentage of subjects with either a pre-vaccination HI (or MN) titer $< 1:10$ and a post-vaccination HI (or MN) titer \geq

Statistical Analysis Plan – Final v2.0

Sponsor Name: Seqirus UK Limited
Sponsor Protocol ID: V130_14

1:40 or a pre-vaccination HI (or MN) titer \geq 1:10 and a minimum 4-fold rise in post-vaccination HI (or MN) antibody titer)
= 0, otherwise

Geometric Mean Titer

Serum HI (or MN) antibody levels of all participants will be measured in serum separated from whole blood. Pre- and post-vaccination samples will be titrated, simultaneously. The titer assigned to each sample shall be the geometric mean of n independent determinations

GMT will be based on the following:

- HI(or MN) antibody titer for each strain: All analyses involving HI (or MN) antibody titer (namely group GMT within a vaccine group) will be performed on the log scale and the resultant summary statistic back-transformed to derived GMT

The GMT will be calculated using the following formula:

$$10^{\left[\frac{\sum_{i=1}^n \log_{10}(t_i)}{n} \right]}$$

where n , t_1 , t_2 , K , t_n are n observed immunogenicity titers.

The 95% CIs for GMT will be calculated as $10^{\{M-t_{0.975,n-1}^{SE}\}}, 10^{\{M+t_{0.975,n-1}^{SE}\}}$; where M and SE are the means and standard error of logarithm base 10 -transformed titers, respectively.

Geometric Mean Ratio

GMRs measure the changes in immunogenicity titers within subjects.

The GMR will be calculated using the following formula:

$$10^{\left[\frac{\sum_{i=1}^n \log_{10}\left(\frac{t_{ij}}{t_{ik}}\right)}{n} \right]} = 10^{\left[\frac{\sum_{i=1}^n (\log_{10}(t_{ij}) - \log_{10}(t_{ik}))}{n} \right]}$$

where, for n subjects, t_{ij} and t_{ik} are observed immunogenicity titers for subject i at time-points j and k, $j \neq k$. The 95% CI for GMR will be calculated as $10^{\{M-t_{0.975,n-1}^{SE}\}}, 10^{\{M+t_{0.975,n-1}^{SE}\}}$; where M and SE are the means and standard error of $\log 10(t_{ij}) - \log 10(t_{ik})$ respectively.

6.6.2 Season Subgroup Analysis

The immunogenicity analyses will be performed for each season by stratifying for the following subgroups:

- Subjects aged “6 through 23 months” and “24 through 47 months”.
- Subjects with pre-vaccination HI (or MN) titer <1:10 and pre-vaccination HI (or MN) titer \geq 1:10.
- Subjects “previously influenza vaccinated” and “not-previously influenza vaccinated”.
- Subjects by race.
- Subjects by sex.
- Subjects by country or region.

6.7 Safety

6.7.1 Secondary Safety Endpoints Analysis

6.7.1.1 Extent of Exposure

The number of subjects actually receiving vaccination will be summarized by study vaccine group on the Enrolled Set.

6.7.1.2 Analysis of Solicited Local, Systemic and Other Adverse Events

Definitions

For details refer to section 7.1.1 of Study Protocol.

Analyses

All solicited adverse events will be summarized according to defined severity grading scales using Solicited Safety Set.

Frequencies and percentages of subjects experiencing each adverse event will be presented for each symptom severity. Summary tables showing the occurrence of any local or systemic adverse event overall and at each time point will also be presented.

Post-vaccination solicited adverse events reported for 7 days after each vaccination will be summarized for the interval day 1-7 by maximal severity and by vaccine group, excluding the 30-minute measurement, which will be summarized separately. Local and systemic AEs:

Statistical Analysis Plan – Final v2.0

Sponsor Name: Seqirus UK Limited
 Sponsor Protocol ID: V130_14

Injection-site erythema, ecchymosis and induration will be summarized according to categories based on linear measurements: Type I: None (0 mm), Any (1-9 mm, 10-25 mm, 26-50 mm, >50 mm).

Injection site tenderness and systemic adverse events (except fever) occurring up to 7 days after each vaccination will be summarized according to “mild”, “moderate” or “severe” categorization. Severity grades are defined in Table 4 below.

Table 5 Solicited Systemic AE Grading

Symptom	Grading			
	0 (None)	Mild (Grade 1)	Moderate (Grade 2)	Severe (Grade 3)
Solicited Local AEs*				
Tenderness		For subjects less than 24 months of age at the time of the first dose of study vaccine:		
Tenderness		Minor reaction on touch	Cried/protested on touch	Cried when limb was moved/ spontaneously painful
Tenderness		For subjects 24 months of age and older at the time of the first dose of study vaccine:		
Tenderness		Does not interfere with daily activities	Interferes with daily activities	Prevents daily activity
Solicited Systemic AEs**				
Change of eating habits	None	Eating less than normal for 1 - 2 feeds / meals	Missed 1 or 2 feeds / meals	Missed more than 2 feeds / meals
Sleepiness	None	shows an increased drowsiness	sleeps through feeds / meals	sleeps most of the time and it is hard to arouse him/ her

Statistical Analysis Plan – Final v2.0

Sponsor Name: Seqirus UK Limited

Sponsor Protocol ID: V130_14

Vomiting (throwing up)	None	1 - 2 times in 24 hours	3 - 5 times in 24 hours	6 or more times in 24 hours or requires intravenous hydration
Diarrhoea (loose stools)	Fewer than 2 loose stools in 24 hours	2-3 loose stools in 24 hours	4-5 loose stools in 24 hours	6 or more loose stools in 24 hours or requires intravenous hydration
Irritability	None	Requires more cuddling and is less playful than usual	More difficult to settle	Unable to console
Shivering	None	Present but does not interfere with daily activity	Interferes with daily activity	Prevents daily activity
Temperature***	<38°C	≥38°C to <39°C	≥39°C to <40°C	≥40°C

* Injection-site erythema, ecchymosis, and induration will be summarized according to categories based on linear measurements: Type I: none (0 mm), Any (1-9 mm, 10-25 mm, 26-50 mm, >50 mm).

** Use of antipyretics and analgesics will be summarized by frequency, by type of use (prophylactic versus treatment) and percentage of subjects reporting use.

*** Body temperature will be summarized by 0.5°C and 1.0°C increments from 36.0°C to ≥40°C and will be broken down by route of measurement and by age cohort.

Each solicited local and systemic adverse event will also be further summarized as "none" versus "any". "Any" will include reactions with a diameter of at least 1 mm. Fever is defined as temperature ≥ 38.0°C (≥ 100.4°F).

Implausible measurements will be left out of the analysis, see Section 5.2 of this SAP.

Other solicited AEs:

Use of antipyretics and analgesics will be summarized by frequency, by type of use (prophylactic versus treatment) and percentage of subjects reporting use.

Statistical Analysis Plan – Final v2.0

Sponsor Name: Seqirus UK Limited
Sponsor Protocol ID: V130_14

Body temperature will be summarized by 0.5°C and 1.0°C increments from 36.0°C up to $\geq 40^{\circ}\text{C}$ and will be broken down by route of measurement and by age cohort.

6.7.1.3 Analysis of Unsolicited Adverse Events

Definitions

All AEs will be characterized according to the date of occurrence related to the first vaccination as follows:

- **Non-Treatment Emergent:** start date before the date of first injection of study vaccine. These are reported in the Medical History output.
- **Treatment Emergent:** start date on or after the date of injection of study vaccine or, AE increase in severity, including to "serious" AE.

If start date is equal to the first date of injection, then "timing" variable ("Did event start before or after vaccination?") will be used to define whether the AE occur before or after the injection.

If an AE happened on the same day of first injection and the time stamp is missing, then the AE is assumed to be treatment emergent.

If an AE start date is missing or unknown, the AE will be considered as emergent.

When start and/or end dates of an AE are only partially known, AEs will be categorized as emergent before, during, or after vaccination phase using the following rules:

- If the partial end date is before ($<$) the first vaccination (i.e., year or year & month is/are before the first study vaccination year or year & month) then the AE is not treatment-emergent.
- If the partial start date is equal or after (\geq) the first study vaccination (i.e., year or year & month is/are after or the same as the first study injection year or year & month) then the AE is considered treatment-emergent.

The **maximum event severity** is the greatest severity associated with a preferred term (PT) for a reported AE according to the following order: Mild < Moderate < Severe. Unknown/ Missing severity is considered as severe.

Multiple AEs with the same PT for the same subject are counted only once.

Vaccination-related AEs are those for which the cause has been evaluated by the investigator, and recorded as related.

Analysis of Unsolicited Adverse Events

This analysis applies to all Treatment Emergent adverse events occurring during the study, judged either as probably related, possibly related, or not related to vaccination by the investigator, recorded in AE Case Report Form (CRF), with a start

Statistical Analysis Plan – Final v2.0

Sponsor Name: Seqirus UK Limited
Sponsor Protocol ID: V130_14

date on or after the date of first vaccination. AE starting prior to the first vaccination will be reported in the Medical History output.

The original verbatim terms used by investigators to identify AEs in the CRFs will be mapped to preferred terms using the Medical Dictionary for Regulatory Activities (MedDRA) dictionary. The AEs will then be grouped by MedDRA preferred terms into frequency tables according to SOC. All reported AEs, as well as AEs judged by the investigator as at least possibly related to study vaccine, will be summarized presenting the number and percentage of subjects having one or more events according to system organ class and preferred term within system organ class. These summaries will be presented by vaccination group and period (as defined in section 2.2): treatment period, follow up period and total observation period (Day 1 until study end). When an AE occurs more than once for a subject, the maximal severity and strongest relationship to the vaccine group will be counted.

Separate summaries will be produced for the following categories:

- SAE
- NOCD
- Adverse events/Serious Adverse events that are possibly or probably related to vaccine
- Adverse event leading to study withdrawal or early termination
- Adverse events leading to a medically-attended visit within 30 days after the onset of ILI episode
- Adverse events leading to a medically-attended visit during the treatment period
- Adverse event resulting in death

Data listings of all adverse events will be provided by subject. In addition, adverse events in the categories above will be provided as listed data.

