### 5.1.1 Informed Consent

"Informed consent" is the voluntary agreement of an individual or his/her LAR to participate in research. Consent must be given with free will of choice, and without undue inducement. The individual must have sufficient knowledge and understanding of the nature of the proposed research, the anticipated risks and potential benefits, and the requirements of the research to be able to make an informed decision.

Informed consent following local IRB/EC guidance **must** be obtained before conducting any study-specific procedure (i.e., all of the procedures described in the protocol). The informed consent process may be conducted up to 10 days prior to any study procedure on Visit 1 (see [Section 13.2, Informed Consent Procedures](#)) The process of obtaining informed consent should be documented in the subject source document in addition to maintaining a copy of the signed and dated informed consent.

If a subject's parent(s)/LAR is unable to read, an impartial witness should be present during the entire informed consent discussion. An impartial witness is defined as a person who is independent from study conduct, who cannot be unfairly influenced by those involved with the study, who attends the informed consent process if the subject or the subject's LAR cannot read, and who reads the informed consent form and any other written information supplied to the subject. After the written informed consent form and any other written information to be provided to subjects, is read and explained to the subject's parent(s)/LAR and after the subject's parent(s)/LAR has verbally consented to the subject's participation in the study and, if capable of doing so, has signed and personally dated the informed consent form, the witness should sign and personally date the consent form. By signing the consent form, the witness attests that the information in the consent form and any other written information was accurately explained to, and apparently understood by, the subject's parent(s)/LAR and that informed consent was freely given by the subject's parent(s)/LAR.

All subjects will sign a generic or a separate ICF which includes the possibility of being included into the immunogenicity sub-set study.

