#### **8.4.3.1.3 Analysis of Unsolicited Adverse Events**

This analysis applies to all adverse events occurring during the study, judged either as probably related, possibly related, or not related to vaccination by the investigator, recorded in AE eCRF, with a start date on or after the date of first vaccination. AE starting prior to the first vaccination will only be listed. The original verbatim terms used by investigators to identify adverse events in the eCRFs will be mapped to preferred terms using the MedDRA dictionary. The adverse events will then be grouped by MedDRA preferred terms into frequency tables according to system organ class.

All reported adverse events, as well as adverse events judged by the investigator as at least possibly related to study vaccine, will be summarized according to system organ

class and preferred term within system organ class. These summaries will be presented by vaccination group.

When an adverse event occurs more than once for a subject, the maximal severity and strongest relationship to the study vaccine group will be counted.

Separate summaries will be produced for the following categories:

- Serious adverse events
- NOCD
- Adverse events that are possibly or probably related to study vaccine
- Adverse event leading to study withdrawal or early termination
- Adverse events leading to a medically-attended visit within 30 days after the onset of ILI episode
- Adverse events leading to a medically-attended visit during the treatment period
- Adverse events resulting in death.

Data listings of all adverse events will be provided by subject. In addition, adverse events in the categories above will be provided as listed data.

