6.4.1 Medical History

Medical history will be coded according to Medical Dictionary for Regulatory Activities (MedDRA) version 22.1 or higher and will be displayed by system organ class and preferred term, using the MedDRA internationally agreed order.

The numbers and percentages of subjects with medical history will be presented by MedDRA system organ class (SOC) and preferred term (PT) by vaccine group and overall. Medical history data will be tabulated for Enrolled Set.

For prior vaccination history, the number and percentage of subjects who have ever been vaccinated, who have received at least 2 Seasonal Influenza Vaccinations prior to current influenza season and who have been assigned to receive 1 or 2 vaccinations during the study, based on the previous vaccination history, will be summarized.

Adverse events that occur between the time the ICF was signed and administration of first vaccination are recorded on the AE form. These events will be reported as an output in the Medical History.

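### SAP 6.7.1.3 contradicts itself on AEs that begin before dose 1 and worsen after it: treatment-emergent by the severity clause, yet sent to Medical History by start date

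*SAP*

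**What the plan says.** SAP 6.7.1.3 opens with two definitions. An AE is treatment-emergent if it has a "start date on or after the date of injection of study vaccine or, AE increase in severity", and the clause goes on to include a change to serious. An AE is non-treatment-emergent if it has a "start date before the date of first injection of study vaccine. These are reported in the Medical History output". The second definition makes no exception for later worsening.

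The analysis paragraph in the same section begins "This analysis applies to all Treatment Emergent adverse events occurring during the study". It then adds the condition that the start date be on or after the date of first vaccination, and closes with "AE starting prior to the first vaccination will be reported in the Medical History output". The separate summaries that follow (SAE, NOCD, related, withdrawal, medically attended, death) sit under this scope.

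SAP 6.4.1 says "Adverse events that occur between the time the ICF was signed and administration of first vaccination are recorded on the AE form" and sends those events to the Medical History output, again without an exception. Protocol 8.4.3.1.3 applies the same start-date limit but gives a different destination: "AE starting prior to the first vaccination will only be listed". Protocol 7.1 describes treatment-emergent AEs simply as those occurring after the first study vaccine and has no worsening route.

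**The concern.** For an AE that starts after vaccination, the severity clause is redundant, because the event already qualifies on its start date. The clause does work only for an AE that began earlier and got worse afterwards. That is exactly the event that the start-date limit and the Medical History routing remove. A programmer must ignore either the definition or the filter, and the SAP does not say which.

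The affected interval is real. AE observation begins at consent (Protocol 7.1), and Protocol 5.1.1 says "The informed consent process may be conducted up to 10 days prior to any study procedure on Visit 1". Protocol 4.3 also foresees children whose vaccination is delayed for a transient infection and who are vaccinated later. Such a child could have an AE on the AE form dated before dose 1.

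If such an AE became severe or serious after dose 1 and stayed under its earlier start date, its only summary output would be Medical History, not the on-study safety tables.

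**Working it through.** The SAP gives no figure to reproduce here, so the check is to apply its rules to each type of event.

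| Event | Severity clause | Start-date definition | Analysis paragraph and 6.4.1 | Result |
|---|---|---|---|---|
| A. Starts before dose 1, does not worsen | Not met | Non-emergent | Medical History | Consistent |
| B. Starts before dose 1, worsens after it, one record with the earlier start date | Emergent | Non-emergent | Excluded; Medical History | Contradiction |
| C. As B, but worsening entered as a new record dated at worsening | Not needed | Emergent | Included | Kept in the tables |
| D. Starts after dose 1, then worsens | Redundant | Emergent | Included | Consistent |

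1. Rows A, C and D come out the same with or without the severity clause. It matters only in row B.
2. In row B the analysis paragraph removes the event. An AE on the day of vaccination but timed before the injection would pass the date limit alone. The routing sentence and SAP 6.4.1 still send it to Medical History, because it started before vaccination.
3. The list of separate summaries contains no rule that brings a row B event back. The clause therefore adds nothing to any summary.

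**Row B or row C?** Protocol 5.1.2 and 7.1.2 treat worsening of a condition in the Medical History as an AE. Protocol 7.1.4 says more generally that worsening of a pre-existing event should be reported as an AE, and refers back to those two sections. Neither document says whether an AE already on the AE form gets a new record and start date when it worsens. Protocol 7.1.3 requires AEs to be monitored until resolved, chronic or stable, which fits one continuing record. It describes a mild/moderate/severe grading but no dated grade changes. The choice between B and C is left open.

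**Size.** The documents give no rate. For scale only, assume that 1% to 5% of 3,830 children have an AE open at dose 1 and that 2% to 10% of those worsen:

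- low: 3,830 × 0.01 = 38; 38 × 0.02 ≈ 1
- high: 3,830 × 0.05 ≈ 192; 192 × 0.10 ≈ 19

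That is about 1 to 19 children across both arms with worsening of any grade, before removing those handled as row C. It is not a count of SAEs.

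**A related gap.** SAP 6.7.1.3 treats an AE with a missing start date as emergent. Its end-date exclusion is written for partial dates only. Read literally, an AE with no start date and a complete end date before first vaccination is counted as emergent. This errs towards overcounting.

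**The case against.** The strongest reply is that little is lost in practice. If sites enter worsening as a new AE, which Protocol 7.1.4 can be read to require, the event passes the start-date limit and stays in every table. By-subject listings cover all AEs. SAEs go to the sponsor within 24 hours, and deaths and AE withdrawals also appear as discontinuation reasons. The window is short: at most about 10 days by the consent rule unless vaccination is delayed, and often the same day. The children are in generally good health, and acute febrile illness is an exclusion. The start-date limit comes from the protocol, so the SAP's severity clause is the outlier. There is no safety hypothesis or success criterion.

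All of this stands as a limit on the consequences. It does not settle which SAP sentence governs, and the documents do not guarantee a new record for an AE already on the AE form.

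A reader might go further and infer that worsened events will necessarily leave the SAE and death tables, or that one or two SAEs will be lost. The safety sizing invites this, since it gives 1,723 QIVc children an 82.2% chance of showing a 1-in-1,000 event. The documents do not support that step. The loss depends on how the worsening is recorded, and nothing in them estimates how many worsenings are serious. The illustrative range above covers both arms and all grades, so it cannot be set against a QIVc-only figure.

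**Conclusion.** The SAP rule is wrong as written. The two definitions overlap for AEs that begin before dose 1 and worsen after it, and the start-date limit makes the severity clause ineffective in every summary table.

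The practical effect is conditional on such an AE being kept under its pre-vaccination start date. Few events are likely to be affected, and possibly no SAEs. Those affected would still be listed by subject. Because the rule turns on onset before vaccination in a randomized, observer-blind trial, no bias between arms is evident. Understated SAE or death counts are a possibility that the plan leaves open, not a demonstrated result. The point merits correction before unblinding because it is cheap to fix and otherwise leaves a classification choice to the programmer.

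**What to change.** 1. In SAP 6.7.1.3, limit the non-treatment-emergent bullet to AEs that start before first vaccination and neither increase in severity nor become serious afterwards.
2. Define the analysis scope as all treatment-emergent AEs, drop the extra start-date condition, and restrict the Medical History routing to non-emergent AEs.
3. Make the same exception in SAP 6.4.1.
4. State that post-vaccination worsening of an AE already on the AE form is identified by a new AE record dated at worsening, or by a dated change in severity or seriousness.
5. Record the departure from Protocol 8.4.3.1.3 in SAP section 7, which does not mention it now, or align the protocol.
6. As a minor addition, state that an AE with a missing start date but a complete end date before first vaccination is not treatment-emergent.

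The cost is SAP wording and one derivation flag, and a few more AEs may appear in the tables. Item 4 carries the only real burden: the worsening date must be identifiable in the data. If the eCRF holds no dated change, sites would need a recording convention, so it should not be assumed that no data work is required.
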